| 
NOTES:
 
 • The nominal Week 100 visit refers to the Week 100 visit per eCRF. • Follow-up will be derived only for participants who permanently discontinued study treatment. 
[a] Assessments taken after Week 100 injection at the nominal Week 100 visit will be assigned to Week 104. Adverse events started on the same day as nominal Week 100 visit date will also be assigned to Week 104.
 
[b] Urinalysis: All parameters provided by the central laboratory under the category of urinalysis, including Urine Albumin/Creatinine, Urine Creatinine, Urine pH, Urine Protein/Creatinine, Urine Erythrocytes, Urine Specific Gravity, Urine Leukocytes, Urine Retinol Binding Protein, Urine Phosphate, Urine Creatinine.
 
[c] Lipids: Cholesterol, HDL Cholesterol Direct, LDL Cholesterol Calculation, LDL Cholesterol Direct, Total Cholesterol/HDL Cholesterol Ratio, Triglycerides
 
[d] Analysis windows for parameters with sparse collection are noted.
 | | | |

Table 10 Assessment Windows for Summary of Snapshot Data Up to Week 152— Data Assigned to Maintenance or Extension Phase

| Snapshot Analysis Windows (If no on-treatment viral load data in default window, use expanded window) | | Analysis Timepoint |
|---|--|---------------------------|
| Default | Expanded +6 Week Upper Window^a | |
| Last available recorded value up to and including the date of first Maintenance Phase dose of IP | Last available recorded value up to and including the date of first Maintenance Phase dose of IP | Baseline |
| $2 \leq \text{Study Day} \leq 42$ | $2 \leq \text{Study Day} \leq 70$ | Week 4 |
| $43 \leq \text{Study Day} \leq 84$ | $43 \leq \text{Study Day} \leq 98$ | Week 8 |
| $85 \leq \text{Study Day} \leq 140$ | $85 \leq \text{Study Day} \leq 154$ | Week 16 |
| $141 \leq \text{Study Day} \leq 196$ | $141 \leq \text{Study Day} \leq 210$ | Week 24 |
| $197 \leq \text{Study Day} \leq 252$ | $197 \leq \text{Study Day} \leq 266$ | Week 32 |
| $253 \leq \text{Study Day} \leq 308$ | $253 \leq \text{Study Day} \leq 322$ | Week 40 |
| $295 \leq \text{Study Day} \leq 378$ | $295 \leq \text{Study Day} \leq 378$ | Week 48 |
| $365 \leq \text{Study Day} \leq 420$ | $365 \leq \text{Study Day} \leq 434$ | Week 56 |
| $421 \leq \text{Study Day} \leq 476$ | $421 \leq \text{Study Day} \leq 490$ | Week 64 |
| $477 \leq \text{Study Day} \leq 532$ | $477 \leq \text{Study Day} \leq 546$ | Week 72 |

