| Long-term Follow-up | On-treatment | 
Q8W arm: Date \leq min (LTFU ART start date, max (Date of Last Injection + 63, Date of Last Dose of Oral Study Treatment (CAB+RPV or SOC Bridging) + 1))
 
Q4W arm: Date \leq min (LTFU ART start date, max (Date of Last Injection + 35, Date of Last Dose of Oral Study Treatment (CAB+RPV or SOC Bridging) + 1))
 |
| | Post-treatment | 
Q8W arm: Date $>$ min (LTFU ART start date, max (Date of Last Injection + 63, Date of Last Dose of Oral Study Treatment (CAB+RPV or SOC Bridging) + 1))
 
Q4W: Date $>$ min (LTFU ART start date, max (Date of Last Injection + 35, Date of Last Dose of Oral Study Treatment (CAB+RPV or SOC Bridging) + 1))
 |

NOTE:

- Date = Assessment/Start Date.
- For Sub-study Screening, Thigh Injection and Return to Gluteal Injection phases, the same on-treatment and post-treatment algorithms as those in Extension Phase will be applied.
 - a. Treatment State is determined after data has been assigned to the study phases as defined in Section [15.4.1](#).
 - b. Last injection and/or last dose of oral study treatment (CAB+RPV or SOC bridging) are only applied to participants who permanently discontinued the study treatment. The assessments for participants who did not permanently discontinue the study treatment will be considered 'On-treatment'. For participants continuing into extension phase, all data assigned to maintenance phase per Section [15.4.1](#) will be considered 'On-treatment'.

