| 
 For participants on the Q8W arm, IM dosing is expected to occur at Week 4B and then every 8 weeks from Week 8 onwards for those transitioning from SOC (i.e. those requiring oral lead-in) and every 8 weeks from Day 1 for those transitioning from CAB+RPV Q4W (i.e. those not requiring oral lead-in) in ATLAS. If participants receive reloading dose injection after oral bridging, the next IM dosing is expected to be 4 weeks from the reloading injection and then every 8 weeks onwards. 
 For participants transitioning from SOC on the Q8W arm, if the preceding injection occurs at Week 4B, the Delay in IP injection (days) will be calculated as: $\text{Delay in IP Injection (days)} = \text{Date of Week 8 injection} - \text{date of Week 4B injection} - 28 \text{ days}$ For participants receiving oral bridging medication and then returning to LA injections, if the preceding injection occurs at a reloading dose visit, the Delay in IP injection (days) will be calculated as: $\text{Delay in IP Injection (days)} = \text{Injection date} - \text{date of preceding injection} - 28 \text{ days}$ For participants transitioning from SOC on the Q8W arm, if the preceding injection occurs at a visit later than Week 4B or at non-reloading visit, the Delay in IP injection (days) will be calculated as: $\text{Delay in IP Injection (days)} = \text{Injection date} - \text{date of preceding injection} - 56 \text{ days}$ For participants transitioning from CAB+RPV Q4W in ATLAS on the Q8W arm, if the preceding injection occurs at non-reloading visit, the Delay in IP injection (days) will be calculated as: $\text{Delay in IP Injection (days)} = \text{Injection date} - \text{date of preceding injection} - 56 \text{ days}$ |

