| 
 If the preceding study treatment is oral (e.g. CAB+RPV or SOC oral bridging), the Delay in IP injection (days) will be calculated as: 
 $\text{Delay in IP Injection (days)} = \text{Injection date} - \text{date of last oral dose on/prior to the injection date}$ Delay in IP injection will be grouped into: ≤ 1, 2-3, 4-7, > 7 days. The proportion of participants with HIV-1 RNA ≥ 50 c/mL at Week 48 (Snapshot) will be summarized by last delay in IP Injection. The last delay in IP injection will be the delay in IP injection at Week 48, or the delay in last IP injection prior to Week 48 if a participant did not receive Week 48 injection (i.e. missing visit or withdrawal). The similar analysis will be done for Week 96 and Week 152 timepoints where the proportion of participants with HIV-1 RNA ≥ 50 c/mL at Weeks 96 and 152 (Snapshot) and the delay in IP injection at Weeks 96 and 152 are considered respectively. |

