| 2.20 | Intent-to-Treat Exposed | 207966/primary_15/T2.19 | Summary of Kaplan-Meier Estimates of Proportion of Subjects Without Confirmed Virologic Failure at Week 152 - Treatment Related Discontinuation = Failure | Replace “Week 96” with “Week 152” in row labels. Change the upper bound in the second footnote to be “study day 1092”. | W152 |
| 2.21 | Intent-to-Treat Exposed | 207966/primary_15/T2.20 | Summary of Kaplan-Meier Estimates of Proportion of Subjects Without Confirmed Virologic Failure at Week 152 - Efficacy Related Discontinuation = Failure | Replace “Week 96” with “Week 152” in row labels. Change the upper bound in the first footnote to be “study day 1092”. | W152 |

| Efficacy Tables | | | | | |
|-----------------|-----------------------------|-------------------------|--|---|-------------|
| No. in W152 | Population | IDSL / Example Shell | Title | Programming Notes | Deliverable |
| 2.22 | Intent-to-Treat Exposed | 207966/primary_15/T2.21 | Proportion of Subjects with HIV-1 RNA ≥ 50 c/mL at Week 152 (Snapshot) by Last Delay in IP Injection | Replace 'Week 96' with 'Week 152', and replace "(i.e. missing visit or withdrawal)" with "(e.g. missing visit, remote visit or withdrawal) in the footnote. | W152 |
| 2.23 | Intent-to-Treat Exposed | 207966/primary_15/T2.38 | Summary of Change from Baseline in Plasma HIV-1 RNA (\log_{10} c/mL) by Visit (Maintenance + Extension Phase) | | W152 |
| 2.24 | Intent-to-Treat Exposed | 207966/primary_15/T2.22 | Summary of Plasma HIV-1 RNA (\log_{10} c/mL) by Visit (Maintenance + Extension Phase) | | W152 |
| 2.25 | Intent-to-Treat Exposed | 207966/primary_15/T2.23 | Cumulative Proportion of Subjects Meeting Confirmed Virology Failure Criteria by Visit (Up to Week 152, Maintenance + Extension Phase) | | W152 |
| 2.26 | Intent-to-Treat Exposed | 207966/primary_15/T2.24 | Cumulative Proportion of Subjects Meeting Confirmed Virology Failure Criteria (Maintenance + Extension Phase) | | W152 |
| 2.27 | Confirmed Virologic Failure | 207966/primary_15/T2.25 | Distribution of Quantitative Plasma HIV-1 RNA Results at Suspected and Confirmation of Confirmed Virologic Failure (Maintenance + Extension Phase) | | W152 |
| 2.28 | Intent-to-Treat Exposed | 207966/primary_15/T2.26 | Proportion of Subjects with Plasma HIV-1 RNA < 2 c/mL by Visit (Maintenance + Extension Phase) | | W152 |

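### In the exploratory table of virologic outcome by injection delay, a participant who misses the visit injection keeps the previous injection's delay category, so a gap 23 to 41 days overdue can be shown as on time

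*SAP*

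**What the plan says.** SAP section 15.6.3 (Delay in IP Injection) defines delay as the injection date minus the "date of preceding injection" minus the planned interval. For regular maintenance dosing that interval is 28 days in the Q4W arm and 56 days in the Q8W arm. On categories it says: "Delay in IP injection will be grouped into: ≤ 1, 2-3, 4-7, > 7 days".

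The last delay is that of the Week 48 injection or, failing that, "the delay in last IP injection prior to Week 48 if a participant did not receive Week 48 injection (i.e. missing visit or withdrawal"). For later timepoints: "The similar analysis will be done for Week 96 and Week 152 timepoints". The footnote to Table 2.21 (Weeks 48 and 96, section 15.15.5.2) repeats the rule. Table 2.22 (section 15.15.6.2), titled "Proportion of Subjects with HIV-1 RNA ≥ 50 c/mL at Week 152 (Snapshot) by Last Delay in IP Injection", keeps it and widens the bracket to "e.g. missing visit, remote visit or withdrawal".

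Two other provisions decide who contributes an outcome. Note b to Table 20 (section 15.4.2) says: "The assessments for participants who did not permanently discontinue the study treatment will be considered 'On-treatment". Table 10 (section 15.3.2) sets the Week 48 Snapshot window at Study Days 295 to 378.

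**The concern.** The delay formula needs an injection date, so a missed injection has no delay of its own, and the four categories have no place for it. For a participant injected at the visit, the tabulated delay is the gap leading up to that visit. For one who missed it, the tabulated delay is the gap one interval earlier. One column therefore mixes two different exposures, and the participant's current gap is not shown.

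I found no other planned table that sets injection delay against Snapshot outcome. In a trial that compares dosing intervals, readers are likely to use this one to judge how late dosing relates to virologic failure. With few failures per category, a few participants in the wrong row can change the rates.

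**Working it through.** The SAP gives no figure to reproduce here. The check applies its own definitions to a participant whose previous injection was on time.

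**Inputs**
- Target study day = 7w + 1 (section 15.3.1). Weeks 40, 44, 48, 52 and 56 fall on Days 281, 309, 337, 365 and 393.
- Planned interval: 28 days (Q4W), 56 days (Q8W) (section 15.6.3).
- Upper end of the Week 48 Snapshot window: Day 378 (Table 10).
- Days overdue = viral load day − last injection day − planned interval.

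**Week 48 injection missed, treatment not discontinued, no oral bridging**

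| | Q4W (last injection Day 309) | Q8W (last injection Day 281) |
|---|---|---|
| Delay used by the SAP | 0, shown as ≤1 day | 0, shown as ≤1 day |
| Overdue at Day 360 | 360 − 309 − 28 = 23 | 360 − 281 − 56 = 23 |
| Overdue at Day 378 | 378 − 309 − 28 = 41 | 378 − 281 − 56 = 41 |
| Delay of next scheduled injection | Week 52: 365 − 309 − 28 = 28 | Week 56: 393 − 281 − 56 = 56 |

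Had the same dose been given on Day 360 and recorded as the Week 48 injection, its delay would be 23 days and the category >7 days. The maximum is the same at the later timepoints. For Q8W at Week 96, 714 − 617 − 56 = 41. For Q8W at Week 152, 1106 − 1009 − 56 = 41.

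**Direction of the distortion**

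This part rests on assumptions that are not in the SAP:
- 510 per arm, with 5% missing the visit injection (25.5 participants), who have the same mix of previous delays as everyone else
- 70/12/13/5% of participants in the four categories, with failure 1.5/1.5/2/4%
- failure among the missed, f, from 0% to 20%

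Under the SAP rule each category absorbs the missed in proportion. The contrast (>7 minus ≤1 day) is 0.95 × (4% − 1.5%) = 2.38 points whatever f is. As a benchmark only, move all the missed into >7 days. That category then holds 484.5 × 0.05 = 24.225 injected participants with 0.969 expected failures, plus the 25.5 missed. The contrast becomes (0.969 + 25.5f)/49.725 − 1.5%.

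| f | SAP rule | Missed moved to >7 days |
|---|---|---|
| 0% | +2.38 | +0.45 |
| 1.5% | +2.38 | +1.22 |
| 5% | +2.38 | +3.01 |
| 10% | +2.38 | +5.58 |
| 20% | +2.38 | +10.71 |

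The two agree at f = (0.03875 × 49.725 − 0.969)/25.5 = 3.8%. Below that the SAP rule overstates the contrast, and above it the rule understates it.

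**The case against.** The strongest reply is that the worked case is uncommon and the table is minor. Viral load and injection are scheduled at the same visit. After a missed Week 48, the next Q8W visit (Day 393) lies outside the window, and the Q4W Week 52 HIV-1 RNA sample is for storage only. The case therefore needs an unscheduled, catch-up or retest sample. That stands as a limit on frequency, which the SAP does not let us estimate, but it does not make the row assignment correct.

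Three further limits also stand:
- **Withdrawals.** After permanent discontinuation without later oral dosing, on-treatment time ends 35 days (Q4W) or 63 days (Q8W) after the last injection. That is at most 35 − 28 = 7 or 63 − 56 = 7 days overdue. No later injection exists, so the previous delay is a defensible exposure.
- **Oral bridging.** A missed injection covered by oral bridging is not an untreated gap.
- **Status.** Table 3 (section 7.3) lists the analysis as an exploratory summary, and the rule is disclosed in the footnote.

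It can also be said that the per-protocol analysis covers under-dosing. Its threshold is 10% of time on treatment. The worked gap alone gives (79 − 63)/360 = 4.4% for Q8W at Day 360 and (97 − 63)/378 = 9.0% at Day 378, so by itself it would not exclude the participant.

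A reader might infer that the rule puts the longest gaps as a class into the on-time row and so biases the table towards no effect. The SAP does not support this. Participants inherit whatever category their previous injection had, and that is ≤1 day only if it was on time. Those still on study with no viral load in the window are classed as having no virologic data (section 15.9). They enlarge the inherited denominator without adding failures, which lowers that row's rate.

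**Conclusion.** The point holds in a limited form. For participants who miss the visit injection without permanently discontinuing and without oral bridging, the table shows the wrong gap. With an on-time previous injection and an in-window viral load between Day 360 and Day 378, someone 23 to 41 days overdue is reported as ≤1 day, in either arm. The day counts follow from the SAP's own target days, intervals and window, and equivalent cases arise at Weeks 96 and 152.

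The effect on the failure rates is of unknown size and direction, because the SAP gives neither the number of missed injections nor their outcomes. The illustration shows only that either direction is possible under plausible inputs. No confirmatory result is touched. The correction is still worth making because the adherence summary in section 15.6.4 already shows missed injections separately, with and without oral bridging. The same participant can therefore be a missed injection in one table and on time in another.

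**What to change.** In section 15.6.3 and the footnotes to Tables 2.21 and 2.22, restrict the four delay categories to participants who received the injection at the analysis visit. At Weeks 48, 96 and 152, show the others in three added rows:
- visit injection missed, no oral bridging
- visit injection missed, with oral bridging
- withdrawn or discontinued before the visit

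If the Week 48 or Week 96 outputs already exist, a supplementary table is enough.

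Do not derive a delay from the date of the viral load that sets the Snapshot outcome. Results above 50 c/mL at these visits lead to a retest within 4 weeks (schedule of activities, footnote l), and Snapshot uses the last value in the window. A high result would therefore lengthen the computed delay and make the exposure depend on the outcome. Such a delay is also undefined when the window holds no viral load.

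The cost is a change to the derivation wording and three table rows from data already held. The downside is slightly sparser cells.

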15.6.4. Safety

| | | | | | | | | | | | | | | | | | | | | | | | |
|--|--------------------------|--|--------------------------------|------------------|-----------------------------|--------------------|-------------------------|----------------|---------------|----------------------|---------------------------|--|------------------------------------|----------------------------------|--------------------------------------|-----------------------|----------------------|--------------|---------|------------------------|--------------------------|---------------------|-----------------------------|
| Adverse Events | | | | | | | | | | | | | | | | | | | | | | | |
| DAIDS Grading | | | | | | | | | | | | | | | | | | | | | | | |
| 
 Clinical adverse events will be graded based on the Division of AIDS Table for Grading the Severity of Adult and Pediatric Adverse Events Version 2.1, March 2017, as specified in the protocol Appendix 11.2. | | | | | | | | | | | | | | | | | | | | | | | |
| Potential QTc Interval Prolonging Events of Interest | | | | | | | | | | | | | | | | | | | | | | | |
| 
Potential QTc Interval Prolonging Events of Interest will be identified based on Standardised MedDRA Query (SMQ) for Torsade de pointes/QT prolongation, broad (MedDRA). The terms per this reference are listed below.
 
 
 AE preferred term	
 
 Electrocardiogram QT interval abnormal	
 
 Electrocardiogram QT prolonged	
 
 Long QT syndrome	
 
 Long QT syndrome congenital	
 
 Torsade de pointes	
 
 Ventricular tachycardia	
 
 Cardiac arrest	
 
 Cardiac death	
 
 Cardiac fibrillation	
 
 Cardio-respiratory arrest	
 
 Electrocardiogram repolarisation abnormality	
 
 Electrocardiogram U wave inversion	
 
 Electrocardiogram U wave present	
 
 Electrocardiogram U-wave abnormality	
 
 Loss of consciousness	
 
 Sudden cardiac death	
 
 Sudden death	
 
 Syncope	
 
 Ventricular arrhythmia	
 
 Ventricular fibrillation	
 
 Ventricular flutter	
 
 Ventricular tachyarrhythmia	
 
 | AE preferred term | Electrocardiogram QT interval abnormal | Electrocardiogram QT prolonged | Long QT syndrome | Long QT syndrome congenital | Torsade de pointes | Ventricular tachycardia | Cardiac arrest | Cardiac death | Cardiac fibrillation | Cardio-respiratory arrest | Electrocardiogram repolarisation abnormality | Electrocardiogram U wave inversion | Electrocardiogram U wave present | Electrocardiogram U-wave abnormality | Loss of consciousness | Sudden cardiac death | Sudden death | Syncope | Ventricular arrhythmia | Ventricular fibrillation | Ventricular flutter | Ventricular tachyarrhythmia |
| AE preferred term | | | | | | | | | | | | | | | | | | | | | | | |
| Electrocardiogram QT interval abnormal | | | | | | | | | | | | | | | | | | | | | | | |
| Electrocardiogram QT prolonged | | | | | | | | | | | | | | | | | | | | | | | |
| Long QT syndrome | | | | | | | | | | | | | | | | | | | | | | | |
| Long QT syndrome congenital | | | | | | | | | | | | | | | | | | | | | | | |
| Torsade de pointes | | | | | | | | | | | | | | | | | | | | | | | |
| Ventricular tachycardia | | | | | | | | | | | | | | | | | | | | | | | |
| Cardiac arrest | | | | | | | | | | | | | | | | | | | | | | | |
| Cardiac death | | | | | | | | | | | | | | | | | | | | | | | |
| Cardiac fibrillation | | | | | | | | | | | | | | | | | | | | | | | |
| Cardio-respiratory arrest | | | | | | | | | | | | | | | | | | | | | | | |
| Electrocardiogram repolarisation abnormality | | | | | | | | | | | | | | | | | | | | | | | |
| Electrocardiogram U wave inversion | | | | | | | | | | | | | | | | | | | | | | | |
| Electrocardiogram U wave present | | | | | | | | | | | | | | | | | | | | | | | |
| Electrocardiogram U-wave abnormality | | | | | | | | | | | | | | | | | | | | | | | |
| Loss of consciousness | | | | | | | | | | | | | | | | | | | | | | | |
| Sudden cardiac death | | | | | | | | | | | | | | | | | | | | | | | |
| Sudden death | | | | | | | | | | | | | | | | | | | | | | | |
| Syncope | | | | | | | | | | | | | | | | | | | | | | | |
| Ventricular arrhythmia | | | | | | | | | | | | | | | | | | | | | | | |
| Ventricular fibrillation | | | | | | | | | | | | | | | | | | | | | | | |
| Ventricular flutter | | | | | | | | | | | | | | | | | | | | | | | |
| Ventricular tachyarrhythmia | | | | | | | | | | | | | | | | | | | | | | | |

| |
|--|
| Laboratory Parameters |
| 
 If a laboratory value which is expected to have a numeric value for summary purposes, has a non-detectable level reported in the database, where the numeric value is missing, but typically a character value starting with '<x' or '>x' (or indicated as less than x or greater than x in the comment field) is present, the number of significant digits in the observed values will be used to |

Laboratory Parameters

determine how much to add or subtract in order to impute the corresponding numeric value. If a character value starting with "<=x", then the numeric value will be x.

- Example 1: 2 Significant Digits = '< x' becomes x - 0.01
- Example 2: 1 Significant Digit = '> x' or '>=x' becomes x + 0.1
- Example 3: 0 Significant Digits = '< x' becomes x - 1

Estimate of Glomerular Filtration Rate (GFR) ([Levey, 2012](#))

- Chronic Kidney Disease Epidemiology Collaboration (CKD-EPI) equation [[Levey, 2012](#)] will be used by the central laboratory to provide an estimate of GFR, in mL/min per 1.73 m², as follows:

$$GFR = 141 \times \min\left(\frac{CRT_{mg/dL}}{\kappa}, 1\right)^{\alpha} \times \max\left(\frac{CRT_{mg/dL}}{\kappa}, 1\right)^{-1.209} \times 0.993^{\text{Age}} \times \\ [1.018 \text{ if Female}] \times [1.159 \text{ if Black}]$$

where age (in years) is at time of assessment, $\kappa = 0.7$ if female or 0.9 if male, $\alpha = -0.329$ if female and -0.411 if male, min() indicates the minimum of CRT/k or 1, max() indicates the maximum of CRT/k or 1, and CRTmg/dL is serum creatinine concentration in mg/dL. The serum creatinine concentration in mg/dL is obtained from GSK standard units of $\mu\text{mol/L}$ as $CRT_{\mu\text{mol/L}} = 0.0113 \times CRT_{\text{mg/dL}}$.

- The CKD-EPI GFR will also be calculated using Cystatin C, as follows

$$133 \times \min(Scys/0.8, 1)^{-0.499} \times \max(Scys/0.8, 1)^{-1.328} \times 0.996^{\text{Age}} \times [0.932 \text{ if female}]$$

Where Scys is serum cystatin C mg/Liter, min indicates the minimum of Scr/0.8 or 1, and max indicates the maximum of Scys/0.8 or 1.

Lab Toxicities – DAIDS Grading based on Version 2.1, March 2017, as specified in the protocol of Appendix 11.2.

- Toxicities will be based on the Division of AIDS (DAIDS) grading system, Version 2.1, March 2017, as specified in the protocol of Appendix 11.2
- Toxicity grades provided by the central laboratory do not distinguish between abnormally high or low criteria, when both are relevant for a parameter.
- When summarising toxicity grades for such parameters, they will be categorised as to whether they are above or below the midpoint of normal range.

| Parameter | Below Midpoint for those \geq Grade 1 | Above Midpoint for those \geq Grade 1 |
|----------------|---|---|
| Fasted glucose | Hypoglycemia | Hyperglycemia |
| Sodium | Hyponatremia | Hypernatremia |
| Potassium | Hypokalemia | Hyperkalemia |

National Cholesterol Education Program (NCEP) Lipid Categories

- In addition to DAIDS toxicity grades (see protocol), lipid values will be categorized according to the 2001 NCEP Adult Lipid Guidelines [[Grundy, 2001](#)]

| Laboratory Parameters | | | | | | | |
|---|----------------------|---------------------------------------|--------------------|--|--|--|--|
| Parameter | Value Range (mmol/L) | Value Range (mg/dL) | Category | | | | |
| Triglycerides | <1.70 | <150 | Normal | | | | |
| | 1.70 to <2.26 | 150 to <200 | Borderline High | | | | |
| | 2.26 to <5.65 | 200 to <500 | High | | | | |
| | ≥5.65 | ≥500 | Very High | | | | |
| Total Cholesterol | <5.18 | <200 | Desirable | | | | |
| | 5.18 to <6.21 | 200 to <240 | Borderline High | | | | |
| | ≥6.21 | ≥240 | High | | | | |
| HDL Cholesterol | <1.04 | <40 | Low | | | | |
| | 1.04 to <1.56 | 40 to <60 | Normal | | | | |
| | ≥1.56 | ≥60 | High | | | | |
| LDL Cholesterol | <2.59 | <100 | Optimal | | | | |
| | 2.59 to <3.37 | 100 to <130 | Near/Above Optimal | | | | |
| | 3.37 to <4.14 | 130 to <160 | Borderline High | | | | |
| | 4.14 to <4.92 | 160 to <190 | High | | | | |
| | ≥4.92 | ≥190 | Very High | | | | |
| Percentage change for lipids | | | | | | | |
| The percentage change from baseline is calculated as: | | | | | | | |
| $\% \text{ change from baseline} = \frac{\text{value at Week 48 or 96} - \text{baseline value}}{\text{baseline value}} \times 100\%$ | | | | | | | |
| Total Cholesterol / HDL Cholesterol Ratio | | | | | | | |
| 
 When both total cholesterol and HDL cholesterol results are available from the same date for a participant, then the ratio will be calculated by dividing the total cholesterol result by the HDL cholesterol result. The ratio can be classified as follows: | | | | | | | |
| Parameter | Value Range | | | | | | |
| | Total Cholesterol | | | | | | |
| | < 3.5 | | | | | | |
| | 3.5 to < 4.4 | | | | | | |
| | 4.4 to < 5 | | | | | | |
| | ≥ 5 | | | | | | |
| Other Safety Endpoints | | | | | | | |
| Corrected QT (QTc) | | | | | | | |
| When not entered directly in the eCRF, corrected QT intervals by Bazett's (QTcB) and Fridericia's (QTcF) formulas will be calculated, in msec, depending on the availability of other measurements. | | | | | | | |
| If RR interval (in msec) is provided then missing QTcB and/or QTcF will be derived as | | | | | | | |
| $QTcB = \frac{QT}{\sqrt{RR/1000}}$ | | $QTcF = \frac{QT}{\sqrt[3]{RR/1000}}$ | | | | | |
| where uncorrected QT interval is also measured in msec. | | | | | | | |

Other Safety Endpoints

If RR interval is not provided directly and one of QTcB or QTcF has been entered, then RR interval can be obtained from the above formulas and used to calculate the other correction method value; i.e.,

$$QTcB = \sqrt{\frac{QTcF^3}{QT}}$$

$$QTcF = \sqrt[3]{QT \cdot QTcB^2}$$

Extent of Exposure

- Exposure to CAB+RPV (oral lead-in or oral bridging) and CAB LA+RPV LA will be calculated from the IP eCRF pages.
- For Maintenance Phase:
 - Exposure to oral CAB+RPV (oral lead-in) = IP (oral lead-in) stop date - IP (oral lead-in) start date + 1
 - Exposure to CAB LA + RPV LA = Number of IP injection visits received during maintenance phase (up to but not including injections administered at Week 100)
 - Exposure to SOC oral bridging: Duration of the SOC ART medication taken as oral bridging during the Maintenance Phase. If the SOC oral bridging is taken in different periods during the Maintenance Phase, the duration will be calculated by the sum of the non-overlapped periods.
 - Exposure to CAB+RPV oral bridging: Duration of the CAB+RPV taken as oral bridging during the Maintenance Phase. If the CAB+RPV oral bridging is taken in different periods during the Maintenance Phase, the duration will be calculated by the sum of the non-overlapped periods.
 - Overall exposure to study treatment:

For participants on Q4W arm: min [Date of Latest Maintenance Phase Visit up to and including Week 100, max (Date of Last Injection + 35, Date of Last Dose of Oral CAB+RPV, Date of Last Dose of SOC Oral Bridging)] – min (Start Date for Oral lead-in CAB+RPV, Date of First Study Injection) + 1

For participants on Q8W arm: min [Date of Latest Maintenance Phase Visit up to and including Week 100, max (Date of Last Injection + 63, Date of Last Dose of Oral CAB+RPV, Date of Last Dose of SOC Oral Bridging)] – min (Start Date for Oral lead-in CAB+RPV, Date of First Study Injection) + 1
- Overall exposure to IP = Overall exposure to Study Treatment – Exposure to SOC Oral Bridging
- For Maintenance + Extension Phase
 - Exposure to CAB LA + RPV LA = Number of IP injection visits received during Maintenance Phase and Extension Phase
 - Exposure to SOC or CAB+RPV oral bridging during the Maintenance and Extension Phase will be calculated similarly to that during the Maintenance Phase except that the exposure includes both Maintenance and Extension Phase.
 - Overall exposure to study treatment:

| |
|-------------------------------|
| Other Safety Endpoints |
|-------------------------------|

For participants on Q4W arm: min [Date of Latest Maintenance/Extension Phase Visit, max (Date of Last Injection + 35, Date of Last Dose of Oral CAB+RPV, Date of Last Dose of SOC Oral Bridging)] – min (Start Date for Oral lead-in CAB+RPV, Date of First Study Injection) + 1

For participants on Q8W arm: min [Date of Latest Maintenance/Extension Phase Visit, max (Date of Last Injection + 63, Date of Last Dose of Oral CAB+RPV, Date of Last Dose of SOC Oral Bridging)] – min (Start Date for Oral lead-in CAB+RPV, Date of First Study Injection) + 1

- Overall exposure to IP = Overall exposure to Study Treatment – Exposure to SOC Oral Bridging
- For Thigh Injection Phase
 - Exposure to CAB LA + RPV LA = Number of IP injection visits received during Thigh Injection Phase. Note that the planned Sub-study Week 16 injections belong to Return to Gluteal Injection Phase.
 - The SOC or CAB+RPV oral bridging are not allowed in this phase.
 - Overall exposure to IP:

For participants on Q4W arm: min [Date of Latest Thigh Injection Phase Visit up to the Nominal Sub-study Week 16 Visit Date, max (Date of Last Injection + 35, Date of Last Dose of Oral CAB+RPV, Date of Last Dose of SOC Oral Bridging)] – Date of First Thigh Injection) + 1

For participants on Q8W arm: min [Date of Latest Thigh Injection Phase Visit up to the Nominal Sub-study Week 16 Visit Date, max (Date of Last Injection + 63, Date of Last Dose of Oral CAB+RPV, Date of Last Dose of SOC Oral Bridging)] – Date of First Thigh Injection + 1

Note that the Nominal Sub-study Week 16 visit date is defined in Section [15.6.1](#).
 - Overall exposure to IP = Overall exposure to Study Treatment.
- For Thigh Injection + Return to Gluteal Injection Phase
 - Exposure to CAB LA + RPV LA = Number of IP injection visits received during Thigh Injection or Return to Gluteal Injection Phase. Note that the injections received on the date of Sub-study Week 24 visit belong to the Extension Phase in main study.
 - The SOC or CAB+RPV oral bridging are not allowed in these two phases.
 - Overall exposure to IP:

For participants on Q4W arm: min [End of Sub-study Date, max (Date of Last Injection + 35, Date of Last Dose of Oral CAB+RPV, Date of Last Dose of SOC Oral Bridging)] – Date of First Thigh Injection) + 1

For participants on Q8W arm: min [End of Sub-study Date, max (Date of Last Injection + 63, Date of Last Dose of Oral CAB+RPV, Date of Last Dose of SOC Oral Bridging)] – Date of First Thigh Injection + 1

Note that the End of Sub-study Date is defined in Section [15.6.1](#).
 - Overall exposure to IP = Overall exposure to Study Treatment.
- Last Injection and/or Last Dose of Oral CAB+RPV and/or Last Dose of SOC Oral Bridging are only applicable to those who permanently discontinued study treatment.

| Other Safety Endpoints |
|--|
| 
 Duration of dosing in participant years will be calculated as the sum of participant duration of dosing in days (across all participants)/365.25 Participants who were randomized but did not report an IP start date will be categorised as having zero days of exposure. |
| Adherence to CAB/RPV Injection Schedule |
| 
Timeliness of Injections relative to Date of Projected Dosing Visits are assessed by using "actual injection visit date - projected visit date from first injection". The injections of interest in adherence analysis are those after first injection. For participants requiring the oral CAB+RPV lead-in, the first injection is planned to be taken at Week 4B. For participants not requiring the oral CAB+RPV lead-in, the first injection is planned to be taken at Baseline/Day 1. For participants receiving the oral bridging and then returning to injections, if the first injection upon return is a reloading dose injection, the immediate next injection visit is planned to be four weeks after the reloading injection visit. If a participant has multiple oral bridging episodes, he or she may have more than one reloading dose injection visits during the study. Each injection visit is counted only once. Individual CAB and RPV injections administered at the same visit are not counted twice. "Extra" unscheduled injections are excluded from all derivations. For example, if during a scheduled visit a participant receives 1 ml of injection instead of 2 ml due to a dosing error, but this participant returns one week later for the remaining 1 ml injection, then the additional visit is excluded. If a participant receives an extra injection at an unscheduled visit by mistake, this visit will also be excluded.
 
The categories of Timeliness of Injections relative to Date of Projected Dosing Visits for summary are listed below:
 
 < -14 days -14 to - 8 days -7 to - 4 days -3 to -2 days -1 day 0 day 1 day 2 to 3 days 4 to 7 days 8 to 14 days >14 days Missed Reloading Injection (Non-COVID-19) Missed Reloading Injection (COVID-19) Missed Injection w/o OB (Non-COVID-19) Missed Injection w/o OB (COVID-19) Missed Injection with CAB+RPV OB (Non-COVID-19) Missed Injection with CAB+RPV OB (COVID-19) |

| Other Safety Endpoints |
|--|
| Missed Injection with SOC OB (COVID-19) |
| Columbia Suicide Severity Rating Scale (C-SSRS) |
| 
Missing data will not have any imputation performed (Nilsson, 2013). |

